7.2 Participant Discontinuation/Withdrawal from the Study

Participants are free to withdraw from participation in the study at any time upon request.

An investigator may discontinue or withdraw a user subject from the study for the following reasons:

- Significant biocontainment device use non-compliance
- If any clinical adverse event (AE) or ADE, or other medical condition or situation occurs such that continued participation in the study would not be in the best interest of the participant
- If the participant meets an exclusion criterion (either newly developed or not previously recognized) that precludes further study participation
- Participant unable to participate with device use for > 2 weeks.

An investigator may discontinue or withdraw a patient subject from the study for the following reasons:

- If any clinical adverse event (AE) or ADE, or other medical condition or situation occurs such that continued participation in the study would not be in the best interest of the participant
- If the participant meets an exclusion criterion (either newly developed or not previously recognized) that precludes further study participation

The reason for participant discontinuation or withdrawal from the study will be recorded on the Study Withdrawal Case Report Form (CRF). Patient subjects who sign the informed consent form and are randomized to use the biocontainment device but do not utilize the biocontainment device may be replaced. Patient subjects who sign the informed consent form and are randomized and use the biocontainment device, and subsequently withdraw, or are withdrawn or discontinued from the study, will be replaced.

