1.3 Schema

Week 1 through Week 4	Enrollment and Training

 • Total n=5 anesthesiologists, 10 CRNAs/anesthesia residents/fellows (user subjects) • Identify user subjects - anesthesiologists and their teams of CRNAs, anesthesia residents and fellows performing planned airway procedures under general anesthesia. • Obtain informed consent from willing user subjects and complete intake questionnaire • Document and record contact information for user subjects • Review user manual and device use. 	
Week 1 through Week 6	Device Use and Assessment

 • Protective device use and aerosol evacuation during airway procedures under general anesthesia on COVID-19-negative patients • Patients (patient subjects) of anesthesiologists participating as user subjects in the study will be recruited on the day of procedure. • Patient subjects will be randomized to intubation with or without the biocontainment device. • Goal of obtaining data from 150 airway procedures under general anesthesia in the device (100 with the device and 50 without the device). • Patient subject Data and data from record of airway procedure will be recorded after each device use • Quality Use Survey, including documentation of any AEs will be completed by user subjects at the end of each day • Patient experience questionnaire completed by patient subject randomized to device use within 1 week after procedure 	

- AE event summary reconciliation and review performed weekly
- Feedback on quality use data use and user suggestions given to engineering team every two weeks
- Interval assessment by the medical director of intubation data from medical record, quality use survey data, including summary of AEs, and preliminary analysis of post-training questionnaire/intake data every two weeks

Week 4 through Week 12	Device Use and Assessment, Final Data Analysis
	
• Continued use and assessment of biocontainment device if needed to meet enrollment numbers• Final Feedback on device use and user suggestions given to engineering team• Final assessment of survey data and device utilization

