5.2 Exclusion Criteria

An individual who meets any of the following criteria will be excluded from participation in this study.

A) User Subjects (healthcare workers):

1. Pregnancy (due to potential risks from lifting the device)

B) Patient Subjects:

1. Known history of difficult airway
2. Anticipated difficult airway management for any reason
3. COVID-19 positive status
4. Planned prolonged intubation post-surgery or anticipated inability to answer patient questionnaire within 1 week of intubation.

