6.3 Measures to Minimize Bias: Randomization and Blinding

Randomization will be done to assign patients to intubation with or without the biocontainment device in a 2:1 fashion. This will allow for analysis of patient-related intubation factors as well as user-related intubation factors as part of the feasibility analysis. Blinding is not possible with this study as all users and patients will be aware of the presence of the device intervention. To help minimize bias in the data analysis, results of all data analysis will be assessed by a neutral, third-party with expertise in statistical analysis.

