8.3.2 Classification of an Adverse Event

8.3.2.1 Severity of Event

Adverse events will be classified based on the defined grading system:

- Mild: events require minimal or no treatment and do not interfere with the participant's daily activities
- Moderate: events result in low level of inconvenience or cause some inference with functioning
- Severe: events interrupt a participant's usual daily activity. Severe events are usually potentially life-threatening or incapacitating. Please note, the term "severe" does not necessarily equate to "serious".

8.3.2.2 *Relationship to Study Intervention*

All adverse events (AEs) and ADEs must have their relationship to the study device assessed by the PI who examines and evaluates the participant based on temporal relationship and his/her clinical judgment. The degree of certainty about causality will be graded using the categories below. In a clinical trial, the study product must always be considered.

- Definitely Related – The AE/ADE is known to occur with the device.
- Probably Related – There is a reasonable possibility that the device caused the AE, or there is a temporal relationship between the device use and event. Reasonable possibility means that there is evidence to suggest a causal relationship between the device and the AE/ADE.
- Possibly Related - There is a possibility that the device caused the AE, or there is a temporal relationship between the device use and event. There is no evidence to suggest a causal relationship between the device and the AE/ADE but an alternate etiology has not yet been established.
- Unrelated – There is not a reasonable possibility that the use of the device caused the event, there is no temporal relationship between the use of the device and event onset, or an alternate etiology has been established.

8.3.2.3 *Expectedness*

Expected adverse events associated with this study that will be tracked and reported include:

1. Minor injury to the patient subject or provider
2. Patient claustrophobia
3. Patient anxiety
4. Difficulty performing intubation with the device in place
5. Need to remove the biocontainment device to safely perform intubation

Potential SAEs associated with this study would include:

1. Major physical injury to patient or provider due to device failure.

A UADE for this device would be breakdown or malfunction of the device during use.

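### Section 7.2 sets no cut-off at randomization for finding a patient ineligible, so under open allocation device patients can be re-judged and lost from the procedure-time comparison

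*Combined protocol and SAP*

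**What the plan says.** **Withdrawal.** Section 7.2 lists reasons for which an investigator may withdraw a patient subject. One is "If the participant meets an exclusion criterion (either newly developed or not previously recognized) that precludes further study participation". It is not tied to any time point, such as randomization or the start of the airway attempt.

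**Exclusions.** Section 5.2 gives four for patients. Number 1 is "Known history of difficult airway". Number 2 is "Anticipated difficult airway management for any reason". Number 3 is COVID-19 positivity. Number 4 is "Planned prolonged intubation post-surgery or anticipated inability to answer patient questionnaire within 1 week of intubation".

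**Allocation.** Section 6.3 states: "Randomization will be done to assign patients to intubation with or without the biocontainment device in a 2:1 fashion". It adds: "Blinding is not possible with this study as all users and patients will be aware of the presence of the device intervention". The Schedule of Activities (Section 12.1) places randomization in the airway-procedure column, after a screening and enrolment column.

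**Replacement and analysis set.** Section 7.2 makes replacement optional for patients randomized to the device who do not use it. It makes replacement mandatory for those who use the device and are then withdrawn. It states no rule for controls. Section 9.3 names only a per-protocol dataset, whereas Section 9.4.2 says that all data points are analysed.

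**Safety reporting.** Section 8.3.2.3 lists difficult intubation with the device in place, and "Need to remove the biocontainment device to safely perform intubation", among the expected adverse events to be tracked. Section 8.3.4 runs reporting from consent to study completion.

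**The concern.** Whether an airway is expected to be difficult is a clinical judgement, and it overlaps with what the trial measures: procedure time and trouble intubating with the device. If that judgement can be revisited once the team knows the patient will be in the device, the two arms may stop being comparable. The incentive to reconsider is greater when the device has been assigned than when routine care has. Patients removed this way would tend to be those with the longest device times. Section 9.1 hypothesises equal times with and without the device, so such losses push towards the hoped-for result.

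**Working it through.** The plan gives no figure for the rate of difficult airways, for post-randomization withdrawal or for procedure time, so there is nothing of its own to reproduce here. Its only relevant numbers are the arm sizes, "100 with the device and 50 without the device" (Section 1.3).

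**Step 1: which patients can the clause reach?**

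- *After allocation, before the attempt.* Exclusion 2 turns on anticipation and admits any reason, so the judgement can be remade at this point without straining the text. The safeguard in Section 7.1 (data still collected when device use stops) is written for a user who cannot complete the procedure with the device in place, so it does not clearly apply. If no time is recorded, analysing all data points does not recover one.
- *After the attempt, through a missed history or predictor.* Section 8.1 has airway data, including Mallampati score and hyomental distance, collected after the procedure. The Schedule of Activities also shows baseline data at enrolment, but nothing requires the predictors to be signed off then. One can therefore be recognised once the outcome is known. Videos are deleted within 14 days (Section 10.1.8.1), which limits later checking.
- *Questionnaire part of exclusion 4.* This is arguable. Only device patients receive the questionnaire (Sections 1.3 and 8.1).

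**Step 2: effect on the difficult-airway rate (assumed inputs).** Let p be the true rate in the device arm and f the share of difficult device cases withdrawn and replaced. The rate among retained device patients is

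q = p(1 − f) / (1 − pf).

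For p = 10% and f = 0.5: q = 0.05/0.95 = 5.26%. Against a 5% control rate, the difference is 5.26 − 5.0 = +0.3 points. Device-minus-control differences, in points:

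| Device v control rate | f = 0 | f = 0.25 | f = 0.5 | f = 1 |
|---|---|---|---|---|
| 4% v 2% | +2.0 | +1.0 | 0.0 | −2.0 |
| 10% v 5% | +5.0 | +2.7 | +0.3 | −5.0 |
| 15% v 5% | +10.0 | +6.7 | +3.1 | −5.0 |

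With equal true rates of 2%, 5% or 10% in both arms, f = 0.5 removes about 1, 2.5 or 5 of the first 100 device patients. The retained device rate falls to 1.0%, 2.6% or 5.3%.

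**Step 3: effect on procedure time (assumed inputs).** Take log-normal times with log-SD 0.4, and let difficult cases take three times as long. In units of the median non-difficult time, an arm's mean is exp(0.4²/2) × (1 + 2q) = 1.083 × (1 + 2q). The difference in means is therefore 2.167 × (device rate − control rate). For 10% v 5%:

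- f = 0: 2.167 × 0.05 = +0.108 (simulation of 100 v 50, 10,000 runs: +0.106)
- f = 0.5: 2.167 × 0.0026 = +0.006 (simulation: +0.005)
- f = 1: 2.167 × (−0.05) = −0.108 (simulation: −0.108)

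Simulated median differences are smaller: +0.028, 0.000 and −0.030.

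In seconds, assume a typical time of 45 s and that k of 100 device patients at t seconds are withdrawn and replaced by typical ones. The device mean then falls by k/100 × (t − 45). This gives 2.25 s (k = 3, t = 120), 6.75 s (k = 5, t = 180) or 15.6 s (k = 8, t = 240).

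**The case against.** A reader might infer that any device patient whose airway proves difficult can be declared ineligible and the event struck from the record. The documents do not support that.

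- Exclusions 1 and 2 require a known history or anticipated difficulty. Difficulty first met during the attempt is neither. Exclusion 4 speaks of planned prolonged intubation, so staying intubated after a complication does not meet that part.
- Withdrawal is not erasure. No section says that data already collected are discarded. Section 7.1 keeps a patient in the study, with intubation data collected, when the procedure cannot be done with the device in place. Sections 8.3.2.3 and 8.3.4 keep difficulty and device removal reportable, and Section 9.4.2 presents total event counts.
- The clause applies to both arms. The only asymmetry written into the plan is the replacement rule, and one-sided use is a matter of incentive, not of text.
- The schedule already puts screening before randomization, and reasons for withdrawal go on a case report form, so use of the clause would be visible.
- The planned summary of time is the median, which moves little.

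Most of this stands. It rules out any claim that events leave the safety count after an attempt. It does not close the gap between allocation and the attempt, because no section fixes eligibility once allocation is known. The point about medians helps only in part, since the ANOVA and multiple regression in Section 9.4.2 work on means.

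**Conclusion.** The point holds in limited form and should be fixed, though it is not critical. With open allocation and no cut-off, a patient can be re-judged ineligible after the device is assigned and can drop out of the time comparison and the per-protocol denominators. The direction, if use is selective, favours equal times. The size cannot be derived: every rate, time and withdrawal share above is assumed, and the figures show direction and range only. The clause is a contributing route. The per-protocol set (Section 9.3) and device-only replacement (Section 7.2) are the larger drivers, but correcting those alone would still leave eligibility open to re-judgement between allocation and the attempt.

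**What to change.** 1. In Sections 5.2 and 7.2, state that patient exclusions 1, 2 and 4 are judged and signed off, with a recorded time, before allocation is revealed.
2. Keep the investigator's ability to stop a patient's further participation, including for exclusion 3. Deleting the clause outright would be too broad, because it also covers newly found COVID-19 status and serves to protect participants.
3. Treat ineligibility found after randomization as a protocol deviation. Analyse the patient's procedure time (where a procedure was done) and all events in the assigned arm. A replacement patient may be added but does not remove the original from the analysis.
4. Report post-randomization withdrawals, with reasons, and replacements by arm.
5. Reconcile the per-protocol set in Section 9.3 with the all-data-points statement in Section 9.4.2.

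The cost is protocol wording and one timed signature per patient. Device-arm results may look slightly less favourable. Clinical freedom to remove the device is unchanged.

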7.3 Lost to Follow-Up

A participant will be considered lost to follow-up if he or she fails to complete study questionnaires and is unable to be contacted by the study site staff.

The following actions must be taken if a participant fails to comply with completing the study questionnaires:

- The PI will attempt to contact the participant and assist with completion of the questionnaires and counsel the participant on the importance of completing the surveys and ascertain if the participant wishes to and/or should continue in the study.
- Before a participant is deemed lost to follow-up, the investigator or designee will make every effort to regain contact with the participant. These contact attempts should be documented in the participant's study file.
- Should the participant continue to be unreachable, he or she will be considered to have withdrawn from the study with a primary reason of lost to follow-up.

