Patient Subject Experience Survey: The patient subject's randomized to device use will be asked in the recovery room post-procedure or receive a phone call or email with REDCap survey link from a qualified study coordinator to answer a short patient experience survey where the data will be collected in REDCap and subsequently transcribed into CTMS. Data collected will include: 1) overall comfort in the device, 2) sensation of increased anxiety, 3) sensation of claustrophobia, 4) perceived safety in the device, 5) any difficulties seeing or hearing while in the device, 6) any additional comments or suggestions regarding the experience in the device. All data will be collected on a Likert scale and stored in CTMS.

Patient subjects' medical records medical will be accessed as part of the study. Personal and medical data collected as part of the study will be stored in a de-identified fashion on an institutionally secured and managed network drive and/or computer.

As part of this study, user subjects' medical records will NOT be accessed. Personal data including age, and gender, will be collected as part of the initial data collection instrument and stored in de-identified fashion on an institutionally secured and managed network drive and/or computer.

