9.4.2 Analysis of the Primary Efficacy Endpoint(s)

Primary Endpoints:

1. Assessment of time to complete an airway procedure with or without the biocontainment device. The time is measured as a single quantitative measure at the end of the procedure. The initial starting time (T0) is defined as “time the mask is removed from the patient just prior to initiation of the airway procedure”. End time (T1) is defined as the time that the airway procedure is completed with a secure airway defined as the

time the airway device is secured to the airway circuit. Data will be presented as median amount of time for a given procedure with or without the biocontainment device and statistical significance will be determined by analysis of variance (ANOVA). Additionally, a multiple regression model will be created using covariates of subject user experience, number of prior uses with the device, and patient specific factors (co-morbid conditions, BMI, Mallampati score). This will help determine the critical factors associated with time to use the device.

2. The total number of AEs and ADEs will be presented. This will be broken down by specific AE or ADE. Logistic regression will be used to assess possible contributing factors to AEs or ADEs including subject user experience, airway procedure performed, patient-specific factors (BMI, co-morbid conditions, Mallampati score). We anticipate a low number of AEs/ADEs and as such, statistically rigorous regression analyses may be limited by a low overall number of events.

Statistical analyses will be performed on all data points, however, a sub-analysis will be performed on participants without any missing data points.

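### A device-arm patient who leaves the survey unanswered and cannot be reached is classed as withdrawn and must be replaced, although the procedure time is already recorded; this can happen in one arm only

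*Combined protocol and SAP*

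**What the plan says.** Section 7.3 defines loss to follow-up for a participant who "fails to complete study questionnaires and is unable to be contacted by the study site staff". If contact attempts fail, "he or she will be considered to have withdrawn from the study with a primary reason of lost to follow-up". The section does not distinguish user subjects from patient subjects.

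Section 7.2 has two replacement rules for patients, both about the device arm. Those "randomized to use the biocontainment device but do not utilize the biocontainment device may be replaced", which is discretionary. Those who are "randomized and use the biocontainment device, and subsequently withdraw, or are withdrawn or discontinued from the study, will be replaced", which is not. There is no exception for a patient whose procedure was completed and timed, and no replacement rule for controls.

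The patient survey is limited to the device arm in two places. The schema (1.3) has "Patient experience questionnaire completed by patient subject randomized to device use within 1 week after procedure". Section 8.1 has "The patient subject's randomized to device use will be asked in the recovery room post-procedure or receive a phone call or email".

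Section 9.4.2 says of the primary time endpoint: "The time is measured as a single quantitative measure at the end of the procedure". Section 8.1 takes the length of the procedure from video.

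**The concern.** Read together, 7.3 and 7.2 let a missing survey trigger the enrolment of another patient for a device procedure, even though the first patient's airway procedure has been done and timed. The new patient cannot supply the missing survey answers. What the replacement adds is one more exposure to an investigational device; section 2.3.3 describes the chance of interference with intubation as small but possibly serious.

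The trigger is also lopsided. A control has no patient questionnaire to leave unanswered, so the rule acts on one arm only, and at a point when the primary time outcome already exists. In an unblinded randomized comparison, a one-arm rule that operates after the outcome needs a clear statement of what happens to the replaced patient's data and how the replacement is allocated. The plan gives neither.

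**Working it through.** **Step 1: the chain of rules for a patient who used the device**

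| Event | Device arm | Control arm |
|---|---|---|
| Procedure completed and timed (9.4.2) | yes | yes |
| Patient survey due within a week (1.3, 8.1) | yes | no |
| Survey unanswered, patient reachable (7.3) | contacted and counselled; not automatically withdrawn | cannot occur |
| Survey unanswered, patient unreachable (7.3) | classed as withdrawn | cannot occur |
| Consequence (7.2) | replacement mandatory | no rule |

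Both conditions are needed: the survey is unanswered and the patient cannot be reached.

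**Step 2: the plan's own targets**

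Randomization is 2:1 (6.3) and the target is 150 procedures (1.3): 150 × 2/3 = 100 device and 150 × 1/3 = 50 control. This matches the schema. The only attrition figure is in 9.2, 10–15% for drop-out and screen failure combined, from at least 175 screened: 175 × 0.90 = 157.5 and 175 × 0.85 = 148.75, consistent with about 150. It is not split by arm or cause, so it gives no survey non-response rate.

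**Step 3: extra device patients**

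Let r be the proportion of device patients who do not answer and cannot be reached. This is an assumption. Replacements can be lost in the same way, so the number needed to retain 100 is 100/(1 − r), rounded up.

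| r (assumed) | 100/(1 − r) | Device patients | Extra |
|---|---|---|---|
| 5% | 105.3 | 106 | 6 |
| 10% | 111.1 | 112 | 12 |
| 20% | 125.0 | 125 | 25 |

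At 10%, 111 is not enough, because 111 × 0.9 = 99.9.

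**Step 4: what depends on unstated rules**

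- If replacements go straight to the device arm and controls stay at 50, the ratio becomes 106/50 = 2.12, 112/50 = 2.24 or 125/50 = 2.50 to 1, with totals of 156, 162 or 175.
- If replacements are randomized 2:1, the ratio holds and the total becomes 1.5 × the device number: 159, 168 or about 188.

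**Step 5: is replacement needed for precision?**

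The standard error of a difference in means, in units of a common SD, is √(1/n₁ + 1/n₂). At 100:50 it is 0.173. If the non-responders' times were dropped and not replaced, it would be 0.175 (95:50), 0.176 (90:50) or 0.180 (80:50). Even at 20% the rise is about 4% (0.180/0.173). If the times are kept, nothing is lost. Precision for the time endpoint therefore gives little reason to replace these patients.

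**The case against.** **The trigger is narrow.** A missed survey is not enough; the patient must also remain unreachable after documented attempts. The survey may be done in the recovery room, by phone or by email (8.1), and 5.2 excludes patients not expected to be able to answer within a week. The rate may well be low. This stands, and it is why the figures begin at 5% and are labelled as assumed.

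**Bias is not shown.** A reader might infer that the rule tilts the time comparison in the device's favour: replacements come later, when users are more practised, and survey response decides whose times count. The documents do not support that as a finding. The shift toward later use, and the drift from 2:1, require replacements to be placed directly in the device arm. No text says so, and 6.3 describes patients as randomized 2:1. Selection after the outcome requires the replaced patients' times to be excluded. No text says that either: 9.4.2 plans to analyse every data point, while the per-protocol set in 9.3 leaves the matter open. The regression in 9.4.2 also includes prior device uses, although the ANOVA comparison is unadjusted.

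**More is missing than a secondary endpoint.** Section 8.3.3 uses the patient survey for safety assessment, and 8.3.2.3 lists claustrophobia and anxiety as expected adverse events. A non-responder therefore also lacks patient-reported data for the second primary endpoint; the users' survey records only what providers perceive (8.1). This stands, and the fix must deal with it. It does not justify replacement, which cannot recover that patient's experience.

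**Larger totals break no rule.** Section 9.2 says at least 150 enrolled and at least 175 screened, and foresees changes to the sample size for drop-out; 1.3 allows use to continue to week 12 to meet enrolment. This is correct. The objection to the extra enrolment is that it is avoidable, not that it exceeds a cap.

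**Conclusion.** The point holds in this form: 7.3 and 7.2 together require replacement of a device-arm patient who leaves the survey unanswered and cannot be reached, after the primary procedure time is recorded, and no control can be affected in the same way. What follows directly is extra enrolment and exposure to the investigational device for every such patient: about 6, 12 or 25 further device patients at assumed unreachable non-response of 5%, 10% or 20%. The documents give no rate, so these are illustrations.

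Ratio drift, a move toward more practised device use, and selection after the outcome remain conditional. The first two arise only if replacements bypass randomization; the third arises only if replaced patients' times are left out. The plan settles neither question and should do so before the data are seen. The change is worth making because it is cheap and removes exposures that add little to the time comparison.

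**What to change.** - **Section 7.3:** for patient subjects, class an unanswered survey as missing survey data rather than withdrawal from the study.
- **Section 7.2:** state that a patient whose airway procedure was completed and timed is not replaced because the survey is missing, and stays in the randomized arm for the time analysis.
- **Sections 9.4.2 and 9.4.3:** keep user-reported adverse events for all patients. Report patient-reported anxiety and claustrophobia with survey respondents as the denominator, so that non-response is not counted as absence of an event. Give the response rate beside the patient-experience results.

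The cost is one sentence each in 7.2 and 7.3 and a short reporting rule in section 9. The number of device exposures falls compared with the present text. The downside is fewer than 100 survey responses for the third secondary endpoint and for patient-reported adverse events.
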